5.4 Major protocol deviations and other exclusion criteria

The following protocol deviations in FAS dataset will be considered and documented :

Protocol deviation ID	Deviation text description	Excluded from analysis set
INCL04D	If the DLQI at baseline is less than or equal to 10 or missing.	INCLUDE IN EVERYTHING
INCL04E	If Total BSA involvement affected by Paque type psoriasis at baseline is less than 10 or missing.	INCLUDE IN EVERYTHING
INCL05	Does not fulfill criteria to meet metabolic syndrome definition	INCLUDE IN EVERYTHING
EXCL02	Previous exposure to Secukinumab or any other biologic drug directly targeting IL17A or the IL17A receptor	INCLUDE IN EVERYTHING
EXCL03	Exposure to anti-TNF treatment during 1 year prior to baseline	INCLUDE IN EVERYTHING
EXCL06	History of latex hypersensitivity.	INCLUDE IN EVERYTHING
EXCL08A	Ongoing use of prohibited treatments.	INCLUDE IN EVERYTHING
EXCL08B	Administration of live vaccines 6 weeks prior to baseline (visit 2) or during the study period	INCLUDE IN EVERYTHING
EXCL10A	Patients with diagnosed un-controlled type 2 diabetes	INCLUDE IN EVERYTHING

EXCL10B	Patients treated with pharmacological therapy with Insulin, sulfonylurea agents/analogues, and/or thiazolidinediones/glitazones	INCLUDE IN EVERYTHING
EXCL13C	Serum pregnancy is missing or test not performed however the patient is randomised.	INCLUDE IN EVERYTHING
EXCL17A	Medical history of myocardial infarction	INCLUDE IN EVERYTHING
EXCL19	Serum creatinine level exceeding 2.0 mg/dl (176.8 µmol/L) at screening	INCLUDE IN EVERYTHING
EXCL20	Total white blood cell (WBC) count < 2,500/µl, or platelets < 100,000/µl or neutrophils < 1,500/µl or hemoglobin < 8.5 g/dl at screening	INCLUDE IN EVERYTHING
EXCL22B	History of an ongoing, chronic or recurrent infectious disease, or evidence of tuberculosis infection as defined by a positive QuantiFERON TB-Gold test (QFT) missing at screening	INCLUDE IN EVERYTHING
EXCL22E	Subject randomised with latent tuberculosis though appropriate treatment not initiated per local guidelines	
EXCL23	Past medical history record or current infection with HIV, hepatitis B or hepatitis C prior to baseline (visit 2).	INCLUDE IN EVERYTHING
EXCL24	History of lymphoproliferative disease or any known malignancy or history of malignancy of any organ system treated or untreated within the past 5 years, regardless of whether there is evidence of local recurrence or	INCLUDE IN EVERYTHING

	metastases (except for Bowen's disease, or basal cell carcinoma or actinic keratoses that have been treated with no evidence of recurrence in the past 12 weeks prior to baseline (visit 2); carcinoma in situ of the cervix or non-invasive malignant colon polyps that have been removed).	
COMD01	Use of prohibited medication at any time during the treatment phase of study.	INCLUDE IN EVERYTHING
COMD02	Use of prohibited medication with potential impact on key efficacy and/or safety evaluations at any time during the study after randomization	INCLUDE IN EVERYTHING
COMD03	Use of prohibited medication not meeting the washout period requirement defined per protocol before baseline visit	INCLUDE IN EVERYTHING
TRT02	<2 injections of secukinumab administered by investigator	INCLUDE IN EVERYTHING
TRT04	More than 1 home administration by the subject.	INCLUDE IN EVERYTHING
TRT05	Subject randomised to arm B with no participation in Lifestyle intervention visit during core phase	INCLUDE IN EVERYTHING
TRT06	Missed visit-no drug administered	INCLUDE IN EVERYTHING
TRT07	First drug administration not at date of randomization/drug assignment date	INCLUDE IN EVERYTHING
TRT08	Patient has a 'Home administration' of study drug before visit 7	INCLUDE IN EVERYTHING
TRT10	Patient has been administered IMP at visit 12.	INCLUDE IN EVERYTHING
TRT11	Patient was administered secukinumab outside the study as commercial product instead of IMP prior to V12.	INCLUDE IN EVERYTHING

TRT12	No study drug administered	INCLUDE IN EVERYTHING
TRT13	Treatment not given due to COVID-19	INCLUDE IN EVERYTHING
TRT14	Patient has been administered expired Secukinumab	INCLUDE IN EVERYTHING
OTH06	Missing PASI assessment during the study	INCLUDE IN EVERYTHING
OTH07	Mishandling of secukinumab	INCLUDE IN EVERYTHING
OTH08	If subject of childbearing status='Able to bear children' at demography however urine pregnancy test is not performed or result is not available	INCLUDE IN EVERYTHING
OTH09	Physical examination is not conducted per protocol	INCLUDE IN EVERYTHING
OTH10	Central laboratory analyses not performed at a scheduled visit	INCLUDE IN EVERYTHING
OTH11	Patient included in the study and was on cholesterol or lipid lowering agent in treatment phase without stable dose for at least 12 weeks prior to baseline	INCLUDE IN EVERYTHING
OTH12	Patient included in the study and was on hypertensive drug in treatment phase without stable dose for at least 12 weeks prior to baseline	INCLUDE IN EVERYTHING
OTH13	Patient included in the study and was on glucose lowering agent in treatment phase without stable dose for at least 12 weeks prior to baseline	INCLUDE IN EVERYTHING
OTH15	Subject has missed study extension visit	INCLUDE IN EVERYTHING
OTH17	No study visit performed due to Covid-19 but study drug administered at home	INCLUDE IN EVERYTHING
OTH18	Missed Visit due to COVID-19	INCLUDE IN EVERYTHING

OTH19	Visit not done at study site due to COVID-19	INCLUDE IN EVERYTHING
OTH20	Assessment/Procedure changed due to COVID-19	INCLUDE IN EVERYTHING
OTH22	Study Discontinuation due to COVID-19	INCLUDE IN EVERYTHING

The protocol deviation list is a live document and can be modified during the conduct of the trial. All the protocol deviations effecting patient safety and/or data reliability & efficacy will be considered major in nature and will be documented and included in Quality tolerance limits. The final list and exclusion codes will be confirmed before the CDBL.

5.5 Visit windows and mapping of visits

Visit-windows will be used for safety & efficacy data that is summarized by visit; they are based on the study assessment schedule and comprise a set of days around the nominal visit day. For any assessment there will be a visit window to cover the complete range of days within the study. The analysis visit will be used for listing of visit and period. If a visit falls after the last visit window it is not assigned an analysis visit and will be listed under label “After Week 56”

Table 5-1 Assessment windows for scheduled visits

Analysis Visit	Week	Scheduled Day	Visit Window
Baseline	BSL	1	-28 days to Day 1
Week 1	1	8	Day 2-11
Week 2	2	15	Day 12-18
Week 3	3	22	Day 19-25
Week 4	4	29	Day 26-43
Week 8	8	57	Day 44-71
Week 12	12	85	Day 72-88
Week 16	16	113	Day 89-127
Week 20	20	141	Day 128-155
Week 24	24	169	Day 156-183
Week 28	28	197	Day 184-211
Week 36 (E1)	36	253	Day 212-295
Week 44 (E2)	44	309	Day 296-379
Week 56 (E3)	56	393	Day 380-435

5.5.1 Multiple assessments within visit-windows

When there are multiple assessments in a particular visit-window, the following rules are applied to select one value “representing” the patient in summary statistics in a visit-window. The baseline value is represented by the last observation prior to the first dose unless otherwise specified.

For baseline assessment definition see [Section 2.1.1.2](#).

For post-baseline visit-windows the following applies (unless otherwise specified):

- for quantitative variables, the closest to the actual visit is chosen (if two assessments have the same distance, then the earlier one will be chosen);
- for qualitative variables, the worst record is selected. It is noted that in the analyses performed, worst case is always well defined.
- in case qualitative variables are based on quantitative variables, e.g. PASI 75 response, the visit will be assigned to the quantitative variable, and this visit will be used for the derived qualitative variable.

6 Reference

Al-Mutairi N, Nour T (2014) The effect of weight reduction on treatment outcomes in obese patients with psoriasis on biologic therapy: a randomized controlled prospective trial. Expert Opin Biol Ther; 2014;14:749-56

Finlay AY and Khan GK (1994) Dermatology Life Quality Index (DLQI): A simple practical measure for routine clinical use. Clin Exp Dermatol; 19: 210-216.

Clinical Development

CAIN457A/METABOLYX

CAIN457ADE08

A randomized, multicenter 28 week study to compare the efficacy and safety of combining Cosentyx (Secukinumab) (4-weekly, 300 mg s.c.) with a lifestyle intervention to Cosentyx therapy alone in adult patients with moderate to severe plaque-type psoriasis and concomitant metabolic syndrome, followed by a 28 week extension period

Biomarker Sub-study Statistical Analysis Plan (SAP)

Author:	
Document type:	SAP Documentation (Biomarker sub-study)

The purpose of the Statistical Analysis Plan (SAP) is to describe the implementation of the statistical analysis for biomarker sub-study as planned in section 9.6 in the clinical study protocol version 00 for the clinical trial CAIN457ADE08 (METABOLYX). Additional analyses, specifications or deviations from the study protocol planned before database lock will also be discussed in this SAP.

1.1 Study design

This study is designed as a randomized, open-label, parallel-group, active comparator-controlled trial with two treatment arms. The design is shown in [Figure 1-1](#).

Figure 1-1 Study Design

R: Randomization

* During the extension period the lifestyle intervention can be continued by patients who have been in arm B during the core study or it can be started by patients who have been in arm A. Participation in the lifestyle intervention during the extension period is **not** mandatory.

† Participation in the extension period itself is mandatory. Psoriasis treatment during the extension period can be chosen freely by the Investigator. No study drug is supplied during the extension period.

Core study: After providing informed consent patients will be screened for eligibility for a period of 1-4 weeks prior to inclusion into the study. If eligible, patients will then be randomized to one of the two treatment arms, which are the following:

- **Arm A:** Patients in arm A receive a regular induction followed by 4-weekly maintenance treatment with Secukinumab 300 mg s.c. until week 28, where they complete the core study. The last Secukinumab injection is performed at week 24.
- **Arm B:** Patients in arm B receive a regular induction followed by 4-weekly maintenance treatment with Secukinumab 300 mg s.c. until week 28. The last Secukinumab injection is performed at week 24. **In addition to Secukinumab treatment patients in arm B participate in a lifestyle intervention program.**

A biomarker sub-study will be performed during the core study to explore the effect of secukinumab (300 mg, 4-weekly s.c.) combined with lifestyle intervention in comparison to secukinumab alone on biomarkers including but not limited to those linked to lipid, glucose, muscle and bone metabolism, liver fibrosis/steatosis, heart failure, as well as to inflammatory processes in a subgroup of 100 patients (50 treated with secukinumab and lifestyle intervention and 50 treated with Secukinumab alone). At baseline (week 0), week 16 and week 28, the following markers will be assessed using **fasting blood samples**: Free fatty acid serum profile, sThy-1, adiponectin, leptin, insulin, HOMA-IR, proinsulin, IL-6, TNF-alpha, M30 assay, IL-1 beta, IL-1Ra, IL-18, IL-18bp, P1NP, CTX, RANKL, OPG, sclerostin, and NT-proBNP.

The markers will be assessed centrally.

Clinically significant abnormal laboratory values for the following parameters of the biomarker sub-study will also be assessed (only for patients participating in the biomarker sub-study): adiponectin, leptin, insulin, HOMA-IR, proinsulin, IL-6, TNF-alpha, M30 assay, NT-proBNP.

1.2 Study objectives, endpoints and estimands

The exploratory biomarker sub-study objective and endpoints are described in [Table 1-1](#).

Table 1-1 Study objectives and endpoints

Objectives	Endpoints
To explore the effect of Secukinumab (300 mg, 4-weekly s.c.) combined with lifestyle intervention in comparison to Secukinumab alone on biomarkers including but not limited to those linked to lipid, glucose, muscle and bone metabolism, liver fibrosis/steatosis, heart injury, as well as to inflammatory processes in a subgroup of 100 patients (50 treated with secukinumab and lifestyle intervention and 50 treated with secukinumab alone)	At baseline (week 0), week 16 and week 28 the following markers will be assessed: Free fatty acid serum profile, sThy-1, adiponectin, leptin, insulin, HOMA-IR, proinsulin, IL-6, TNF-alpha, M30 assay, IL-1 beta, IL-1Ra, IL-18, IL-18bp, P1NP, CTX, RANKL, OPG, sclerostin, NT-proBNP, CD154, and a 30-panel multiplex inflammatory cytokine and chemokines panel

2 Statistical methods

This section contains information that will be used to draft CSR Section 9.7 on statistical analysis.

2.1 Data analysis general information

All statistical analysis will be performed by Novartis Business Services CONEXTS (NBS CONEXTS). Data will be analyzed by statistical software SAS version 9.4 according to the data analysis section 9.6 of the study protocol.

2.1.1 General definitions

Summary statistics for continuous variables will include N (the number of subjects in the analysis set), n (the number of subjects with available/imputed value), mean, standard deviation (SD), median, minimum & maximum. Summary statistics for discrete variables will be presented in contingency tables and will include absolute and relative frequencies for non-missing data. A row (category) denoted “Missing” will be included in count tabulations if a non-zero count of missing values is present. Percentages will be calculated using the number of patients in the relevant population or subgroup as the denominator. If a count of zero is obtained, the zero count and percentage will still be displayed.

If not otherwise specified, p-values will be presented as two-sided p-values along with the two-sided confidence interval.

Unless otherwise stated, the level of significance will be set to 5% (two-sided).

Change from baseline and percentage change from baseline will only be summarized for subjects with both baseline and post-baseline values and will be calculated wherever applicable as:

Change from baseline = post-baseline value – baseline value.

Percentage change from baseline = ((Change from baseline value) / (baseline value)) * 100

2.1.1.1 Study Treatment and Study Day

The day of randomization visit where the patients were allocated to their respective treatment arm i.e. Arm A or Arm B, respectively is defined as Day 1. All study days will be labelled relative to Day 1. Day 0 will not be used, the day before Day 1 is Day -1.

For events occurring on or after Day 1,

Study day = [Date of event] - [Date of first dose] + 1

For events occurring prior to Day 1,

Study day = [Date of event] - [Date of first dose]

2.1.1.2 Screening, baseline and post-baseline definitions

Screening period refers to the period starting from signing the informed consent until randomization or screening failure. Per protocol, subject informed consent must be obtained prior to performing any study related activity. The date of signing informed consent is the start date of screening period. Any assessment obtained during the screening period will be labeled screening assessment.

For efficacy analyses, baseline is the last available pre-dose assessment obtained at Visit 2. If the measurements at Visit 2 are missing, the measurements obtained at Visit 1 will be considered as the baseline. All assessments obtained after Visit 2 are considered as post-baseline.

For safety analyses, baseline is the last assessment obtained before the first dose of study treatment (i.e. secukinumab) at Visit 2. If the measurements at Visit 2 are missing, the measurement at Visit 1 will be considered as the baseline. All assessments obtained after the first dose of study treatment (i.e. secukinumab) are considered as post-baseline.

2.2 Analysis sets

The following analysis sets will be used for the data analysis.

Safety Set (SAF): The SAF will consist of all patients who received at least one dose of study treatment i.e. secukinumab. Patients will be analyzed according to the treatment they received, i.e. secukinumab alone or secukinumab with life-style intervention.

Biomarker Analysis Set (BAS): The BAS will consist of all patients in the Safety set (SAF), who have been enrolled in the biomarker sub-study & had at least one evaluable biomarker value.

All the statistical analyses for biomarker sub-study will be performed on the BAS dataset.

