2.2 Analysis sets

The following analysis sets will be used for the data analysis.

Enrolled Set (ENR): The ENR will consist of all patients who provided signed and dated informed consent

Randomized Set (RAN): The RAN will consist of all patients who were randomized into this study at baseline. Patients in the RAN will be analyzed according to the treatment they were randomized to.

Safety Set (SAF): The SAF will consist of all patients who received at least one dose of study treatment i.e. Secukinumab. Patients will be analyzed according to the treatment they received, i.e. secukinumab alone or Secukinumab with life-style intervention.

Full Analysis Set (FAS): The FAS will consist of all patients who were randomized into this study at Baseline and received at least one dose of study treatment i.e. Secukinumab. Following the intent-to-treat principle, patients in the FAS will be analyzed according to the treatment assigned at randomization.

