2.4.2.2 Lifestyle intervention

Compliance as percentage of lifestyle intervention visits participated in will be calculated as the number of intervention visits attended (based on documented participation counts as given in the lifestyle intervention record eCRF page) divided by the number of lifestyle intervention visits scheduled per protocol until discontinuation. It is to be noted that for dropouts/discontinuations, the denominator will be adjusted to number of intervention visits participated scheduled per protocol until discontinuation.

It is given by the formula:

Compliance (%) = $100 * (\text{total no of lifestyle intervention visits participated}) / (\text{no. of lifestyle intervention visits scheduled})$

In the core study selection phase lifestyle intervention visit are scheduled at weeks 0, 1, 2, 3, 4, 8, 16 and 24. In the extension study phase the visits are scheduled for weeks 36, 44 and 56. Patients in Arm A starting lifestyle intervention during the extension phase will have their first

lifestyle intervention at week 28. Patients in Arm A do not have a lifestyle intervention at week 56. Patients in Arm B have lifestyle intervention visits at E1, E2 and E3.

Compliance percentage will be summarized for the SAF dataset (displaying totals) by treatment group and also by categories (< 80% and ≥ 80% to 100%).

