5.1 Statistical models

MMRM Model

Absolute biomarkers value will be analyzed using a Mixed Model for Repeated Measurements (MMRM) with factors treatment, center, visit, visit*treatment interaction and covariate baseline biomarker value.

```
proc mixed data = BAS covtest;  
class subjid TRT01P siteid avisitn;  
model CHG_B = base TRT01P siteid avisitn avisitn*TRT01P/ ddfm=KR  
residual;  
repeated avisitn / type=un subject=subjid rcorr;  
estimate "Trt diff at Week 28" Trt 1 -1 TRT01P*avisitn 1 -1/cl;  
lsmeans Trt*VisitWk / cl;  
run;
```

Where,

BAS = dataset; TRT01P = Treatment arms (A & B); CHG_B = Change from Baseline

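### The biomarker SAP groups its analysis set by treatment received while its model code names the assigned arm; if the text is followed, arm B patients who never attend lifestyle would naturally leave arm B

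*SAP*

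**What the plan says.** - **Biomarker SAP 2.2.** The Safety Set (SAF) is grouped as received: "Patients will be analyzed according to the treatment they received, i.e. secukinumab alone or secukinumab with life-style intervention". The BAS is drawn from it: "The BAS will consist of all patients in the Safety set (SAF), who have been enrolled in the biomarker sub-study", with at least one evaluable biomarker value. No separate grouping rule is given for the BAS, and "All the statistical analyses for biomarker sub-study will be performed on the BAS dataset".
- **Biomarker SAP 5.1.** The mixed-model code carries TRT01P as the treatment factor, explained as "TRT01P = Treatment arms (A & B"). The ESTIMATE and LSMEANS lines use a second name, Trt, which is not defined.
- **Main SAP 2.2.** The SAF has the same as-received rule ("Patients will be analyzed according to the treatment they received, i.e. secukinumab alone or Secukinumab with life-style intervention"). For the Full Analysis Set (FAS), however, "patients in the FAS will be analyzed according to the treatment assigned at randomization".
- **Core lifestyle compliance.** Main SAP 2.4.2.2: "Compliance percentage will be summarized for the SAF dataset (displaying totals) by treatment group". Biomarker SAP 2.4.3.2 plans the same table on the BAS.
- **Main SAP 5.4, deviation TRT05.** "Subject randomised to arm B with no participation in Lifestyle intervention visit during core phase". These patients stay in all analysis sets, but the entry does not say in which treatment column.
- **Protocol 9.1.** The SAF is defined only by receipt of a dose. The sentence on assigned treatment follows the FAS definition. Section 4 of neither SAP lists as-received grouping as a change.

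**The concern.** Both arms receive the same drug on the same schedule (protocol 5.2), so only the lifestyle programme separates the two received categories. Attendance is patient behaviour after randomisation. On the natural reading of the rule, an arm B patient with no lifestyle visit received secukinumab alone and moves to the comparator column.

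Two things are then at stake:

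- The biomarker contrasts would compare attenders with a mixture of arm A and arm B non-attenders. If non-attenders have a different metabolic course whatever their arm, a difference appears without any lifestyle effect. Biomarker SAP 2.5.2 disclaims formal testing but still reports confidence intervals and p-values by visit. Its section 2.5.1 lists 19 markers plus 11 fatty-acid molecules, 30 outcomes in all.
- The arm B compliance column would describe only those who attended at least once, which overstates adherence to the randomised intervention.

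**Working it through.** **No stated figure to reproduce.** Biomarker SAP section 3 says that the sub-study has no formal sample size computation. The main-trial figure of 342 per arm reproduces exactly with the continuity-corrected two-proportion formula, and this point does not touch it.

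**Text against code.** The set definition says as received. The code legend says arms A and B, and biomarker SAP 2.1.1.1 describes the arms by allocation at randomisation. The code covers only the mixed model, so disposition, descriptive and compliance tables are left to the set definition. Main SAP 2.8 summarises biomarkers by weight-loss subgroup on the FAS (as randomised); biomarker SAP 2.6 does so on the BAS. The same summary therefore has two possible groupings.

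**Bias if the text is followed.**

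Inputs:
- 50 patients per arm (protocol 6.6.5; main SAP 2.7.5).
- No true lifestyle effect (assumed).
- f = share of never-attenders. The documents do not give it; 4%, 10% and 20% are used.
- d = prognostic gap in SD between attenders and never-attenders, after adjustment for baseline and centre. The documents do not give it; 0.5 is used, with a range of 0 to 0.8.

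Randomisation gives both arms the same expected share f of never-attender types. Moving arm B's share makes the secukinumab-alone group 50(1+f) patients, of whom 100f are never-attender types. The lifestyle group has 50(1−f) patients and none of them. So

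bias = d × 100f / [50(1+f)] = 2fd/(1+f), and SE = √(1/nA + 1/nB) in SD units.

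| f | nA / nB | Bias at d = 0.5 | SE | Bias/SE | Rejection, normal approx. | Rejection, simulated |
|---|---|---|---|---|---|---|
| 4% | 52 / 48 | 0.04/1.04 = 0.038 | 0.200 | 0.19 | 5.4% | 5.2% |
| 10% | 55 / 45 | 0.10/1.10 = 0.091 | 0.201 | 0.45 | 7.4% | 7.2% |
| 20% | 60 / 40 | 0.20/1.20 = 0.167 | 0.204 | 0.82 | 12.9% | 12.5% |

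The simulation used 20,000 two-sample t-tests per row. Grouping as randomised gave rejection of 4.6% to 5.1% and has no bias. With d from 0.25 to 0.8, the bias is 0.02–0.06 SD at 4%, 0.05–0.15 SD at 10% and 0.08–0.27 SD at 20%. At d = 0.8 and f = 20%, rejection reaches 24.0%. At d = 0 there is no bias.

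**Compliance.** Suppose attenders average 85% (assumed). Mean compliance over all dosed arm B patients is (1−f) × 85%: 81.6%, 76.5% and 68.0% at f = 4%, 10% and 20%. With the 0% patients moved out, the column shows 85% in each case.

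**The case against.** A reader might infer that the plan moves arm B non-attenders to arm A and so breaks randomisation. The documents do not go that far. No section defines receipt of lifestyle or says that a non-attender is counted as secukinumab alone. Arm B patients are given the programme materials at visit 2 (protocol 5.5.3.2), so a reading in which all of them received lifestyle is open. The rule may also be meant for allocation errors. TRT01P points to the assigned arm, and the BAS is never expressly said to inherit the SAF grouping. All of this stands, and it makes the finding a conflict and an undefined rule rather than a stated reclassification. It does not remove the problem, because the written set definition points the other way and the code covers only the model.

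It might also be inferred that never-attenders disappear from the report. They do not: main SAP 2.3.1 tabulates major deviations in the Randomized Set, so the TRT05 count stays visible for the whole trial, and the compliance tables display totals and a below-80% category. What could be wrong is the arm B compliance column.

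The direction of bias is not fixed. Patients who discontinue lifestyle may start or change metabolic treatment (protocol Table 5-1 notes and 5.6.2), which could improve their markers.

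Non-attendance may also be rare: motivation is an inclusion criterion, attendance is mandatory, and TRT05 requires no core-phase visit at all. At 4% and 0.5 SD, rejection is essentially nominal.

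**Conclusion.** The point holds as a conflict between the biomarker SAP's set definition and its model code, with no definition of what receiving lifestyle means. If the text governs, the natural result is a non-randomised biomarker comparison and core compliance tables without arm B's 0% attenders. At an assumed 0.5 SD gap, the effect runs from negligible (4% non-attendance) to about 0.17 SD and 13% rejection per marker (20%). Both inputs are assumptions.

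The reach is limited. The sub-study is exploratory. The primary and main secondary analyses use the FAS as randomised and are unaffected. The extension compliance table uses the extension FAS (extension SAP 2.4.2.1), so it is outside this point. The change is still worth making, because a rule as written would bias reported estimates and p-values if followed, and correcting it costs almost nothing.

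**What to change.** 1. In biomarker SAP 2.2, state that all BAS analyses and tables, including descriptive, disposition and weight-loss tables, are grouped by the arm assigned at randomisation.
2. In biomarker SAP 5.1, use one assigned-arm variable throughout the code, replacing the undefined Trt.
3. In main SAP 2.4.2.2 (core phase) and biomarker SAP 2.4.3.2, report lifestyle attendance for all dosed patients randomised to arm B (within the BAS for the latter), with non-attenders at 0%.
4. If as-received grouping is kept for adverse-event tables, define what counts as receiving lifestyle.

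The cost is a few sentences and a code edit, with no new data and no change in sample size. The downside is that reported arm B compliance may be slightly less favourable.
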